3.5.2. Photobiomodulation protocol

The photobiomodulation protocol will be performed using an equipment from Ibramed Equipamentos Médicos® of Aluminized Gallium Arsenide (AsGaAl) laser diode, with a wavelength of 830 nm, fluency of 20 J/cm², 30 mW, beam area of 0.116 cm², energy of 2,3 J

per point, continuous beam (22). The low-level laser therapy (LLLT) will be applied for 30 seconds at one point on the trigger point in upper trapezius, right after the dry needling application.

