**UNIVERSIDADE FEDERAL DE SANTA CATARINA
CAMPUS ARARANGUÁ-ARA**

[name]
[contact] / [name]

RESEARCH PROJECT

Dry Needling and Photobiomodulation in the treatment of Myofascial Pain

Study Principal Investigator: [name] [name].

ABSTRACT

Myofascial Pain is a clinical condition of myalgic pain characterized mainly by the presence of Myofascial Trigger Points. Trigger points can be active or latent and they are described as a hypersensitive spot within a taut band in the muscle. The use of a computer for long periods has been shown as a trigger the trigger points. Dry Needling and Low-Level Laser Therapy (LLLT) has been described as good resources to treat myofascial pain. The hypothesis is that the association of the purposed interventions will have greater effects than only the dry needling intervention. The objective is to evaluate the effects of the dry needling and the laser in the treatment of upper trapezius trigger point on women. This study is composed of an evaluation and an intervention proposal with dry needling and LLLT to treat myofascial trigger points. The sample will be composed of 60 women, with 18 to 65 years old, divided into three groups. Twenty individuals will be in group Dry-On that will receive dry needling intervention on the trigger point, followed by LLLT intervention on. Twenty individuals will be in group Dry-Off that will receive dry needling intervention on the trigger point, followed by LLLT intervention turned off. Twenty individuals will be in group Control that will receive dry needling intervention at 1.5 cm from the trigger point, followed by LLLT intervention turned off. All interventions will be performed in one session. Outcome measures for pain, pressure pain threshold, functionality, and muscle activity will be collected.

Key-words: Myofascial pain; Pressure Pain Threshold; Low-Level Laser Therapy; Dry needling;

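### The laser settings contradict each other: 30 mW for 30 s gives 0.9 J, not the stated 2.3 J, so Group On may receive about 39% of the stated dose

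*Combined protocol and SAP*

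**What the plan says.** The active laser treatment is defined in one paragraph, Section 3.5.2. It specifies a laser diode with a "wavelength of 830 nm, fluency of 20 J/cm², 30 mW, beam area of 0.116 cm², energy of 2,3 J" per point, in continuous mode. The next sentence fixes time and place: "The low-level laser therapy (LLLT) will be applied for 30 seconds at one point on the trigger point in upper trapezius", straight after the needling. The Abstract confirms that nothing accumulates over visits: "All interventions will be performed in one session".

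Section 3.1 defines the arms. Groups On and Off both receive dry needling at the trigger point and differ only in whether the laser is switched on. The Abstract gives the hypothesis that the combination does better than needling alone, and the end of the Introduction repeats it as the study question. No other section gives a power, time, number of points or dose for this trial. The other laser doses, in the Introduction, belong to cited studies.

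**The concern.** Power, time, beam area, energy and fluence are tied together by two identities, so a protocol that states all five can be checked for consistency. This one fails: power and time imply a much smaller dose than the energy and fluence beside them.

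The paragraph defines the only active ingredient that separates Group On from Group Off. Someone who times 30 s at 30 mW delivers one dose; someone who sets the device to 2.3 J or 20 J/cm² delivers another. The protocol does not say which figure governs, and it has no step for recording the energy delivered. Three things are at stake:

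- A null result could be reported as failure of 20 J/cm² when 7.8 J/cm² was given, and a positive result could be credited to the wrong dose.
- Nobody repeating the trial would know what to reproduce.
- Dose could differ between participants if the settings were read in different ways.

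**Working it through.** **Inputs, all from Section 3.5.2 except the number of sessions (Abstract)**

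- Power P = 30 mW = 0.030 W
- Time t = 30 s, at one point
- Beam area A = 0.116 cm²
- Energy per point E = 2.3 J (printed with a decimal comma)
- Fluence F = 20 J/cm²
- Continuous beam, so no duty-cycle factor; one session

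**Identities:** E = P × t and F = E / A.

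**Step 1. Reproduce the stated energy from fluence and area.** F × A = 20 × 0.116 = 2.32 J, within 0.9% of 2.3 J. In reverse, 2.3 / 0.116 = 19.8 J/cm². Energy, fluence and area agree.

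**Step 2. Try to reproduce it from power and time.** P × t = 0.030 × 30 = 0.90 J, which is 61% short of 2.3 J. The matching fluence is 0.90 / 0.116 = 7.76 J/cm².

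**Step 3. Size of the gap.**

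| Quantity | Stated | From 30 mW × 30 s | Stated ÷ derived | Derived as % of stated |
|---|---|---|---|---|
| Energy | 2.3 J | 0.90 J | 2.56 | 39.1% |
| Fluence | 20 J/cm² | 7.76 J/cm² | 2.58 | 38.8% |

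**Step 4. What would have to change.**

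- Keep 30 mW and the stated dose: t = 2.3 / 0.030 = 76.7 s (77.3 s for exactly 20 J/cm²).
- Keep 30 s and the stated dose: P = 2.3 / 30 = 0.0767 W, about 77 mW.
- Keep 30 mW and 30 s: energy becomes 0.90 J, and then fluence or area must change too. Fluence becomes 7.76 J/cm² at 0.116 cm²; holding 20 J/cm² would need an area of 0.90 / 20 = 0.045 cm².

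If exactly one figure is wrong, it is therefore power or time. If both of those are right, at least two other entries are wrong.

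**Step 5. Can another reading close the gap?**

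- *Rounding.* With power within ±0.5 mW, time within ±0.5 s and energy within ±0.05 J, derived over stated energy runs from (0.0295 × 29.5) / 2.35 = 0.37 to (0.0305 × 30.5) / 2.25 = 0.41. Even ±5 mW and ±5 s gives only (0.025 × 25) / 2.35 = 0.27 to (0.035 × 35) / 2.25 = 0.54.
- *Several points or sessions.* The text says one of each.
- *Pulsing.* The text says continuous, and a duty cycle would only lower the energy.

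None of these reconciles the figures.

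**The case against.** The arithmetic is hard to dispute; the consequences can be disputed.

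- **The 39% is only one possibility.** Energy, fluence and area agree, so a single slip would lie in power or time, and the full 2.3 J may be delivered. This stands: the delivered dose is somewhere from about 39% to 100% of the stated dose, depending on which figure is wrong. It does not remove the contradiction. If time is the slip, there is a further consequence: 30 s is the only duration the protocol gives for the switched-off laser, while Group On would need about 77 s, so the length of application could differ between arms.
- **Variation between participants is not shown.** The trial uses one laboratory and one make of laser, and the protocol does not describe several operators. This also stands. Variation is possible because no figure is given priority, but a constant, mislabelled dose is at least as plausible.
- **The randomised comparison survives.** On versus Off remains active laser against laser off, and the hypothesis names no dose. With a constant dose the contrast is valid for that dose. What suffers is the label on the result, its replication and the reading of a null finding. Off versus Control is untouched, and no sample size or alpha figure depends on these values.
- **The lower dose may still work.** The Introduction cites a positive result at 4 J/cm², in a different muscle. It also cites benefit at 2 J given three times a week for four weeks, which is 12 sessions against one here. This evidence is mixed and does not settle whether 0.9 J in a single session is enough.

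These points limit what can be said about harm. They do not make the five figures compatible.

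**Conclusion.** The concern holds. Section 3.5.2 is wrong as written: the stated power and time give 0.90 J and 7.8 J/cm², against a stated 2.3 J and 20 J/cm², a factor of about 2.6. That at least one figure is wrong rests only on the document's own numbers and the two identities. That Group On receives 39% of the stated dose rests on the further assumption that 30 mW and 30 s are what is delivered. The document cannot show which figure was intended. The internal agreement of energy, fluence and area points towards power or time, but that is an inference. The error lies in the definition of the treatment under test, so it bears on what any On-versus-Off result means.

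**What to change.** Before the first participant is treated, the sponsor should decide which figures were intended and restate Section 3.5.2 so that power × time = energy and energy ÷ area = fluence. With the stated beam area, the candidates are:

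- 30 mW for about 77 s, giving 2.3 J and 20 J/cm²;
- about 77 mW for 30 s, giving the same dose, if the device can deliver that power;
- 30 mW for 30 s, giving 0.9 J and 7.8 J/cm².

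State the same application time for the switched-off laser in Group Off and the control group. Check the device display or output against the chosen set, record delivered energy for each participant, and report the dose on that basis. If treatment has already started, establish the settings actually used and report that dose.

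The cost is a one-line protocol correction, a device-setting check and one extra field on the treatment record. No extra participants are needed and the analysis does not change.

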3.5.3. Placebo protocol

The placebo/control group will receive the DN application 1.5 cm away from the trigger point and will follow the application protocol described above. The LLLT equipment will be turned off during the intervention. As the other groups, it will be performed one session of the dry needling followed by the intervention with the laser turned off.

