3. METHODS

3.1. Study Design

The present study is characterized as a randomized clinical trial, controlled, with a proposal of evaluation and intervention of dry needling associated to the low-level laser therapy (LLLT) to treat the trigger point caused by myofascial pain. The subjects will be randomized into three groups:

- Group On: application of dry needling and LLLT turned on directly on the trigger point;
- Group Off: application of dry needling and LLLT turned off directly on the trigger point;
- Placebo/Control group: application of dry needling and LLLT turned off away from the trigger point.

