The Visual Analogue Scale (VAS) will be used so the subjects can graduate their pain in shoulder and neck regions. The VAS level of pain will be acquired before the intervention (baseline), soon after the intervention (T₁), 30 minutes after the intervention (T₂), one week (T₃) and one month (T₄) after the intervention.

Pressure algometry will be used to evaluate the pain pressure threshold (PPT). This measured will be obtained before the intervention (baseline), soon after the intervention (T₁), and 30 minutes after the intervention (T₂). The equipment will be positioned on the trigger point mark and the subject will be instructed to report when the sensation changes from pressure to pain (16). The force measured in kilograms per square centimeter (kg / cm²) will correspond to

the quantity of pressure needed so the subject report change in pressure pain sensation (14). The pressure will increase constantly on 1 kg / cm² / s. It will be collected three measured, with an interval of 20 seconds between each measure, and the average of the three values will be used in data analysis.

The Neck Disability Index (NDI) is a unidimensional questionnaire composed of 10 items that have the aim to evaluate the limitation caused by pain and disability on the neck (30). This questionnaire is organized according to the type of activity performed and express positive levels of functional capability. Its score ranges from 0 to 50, where 0 to 4 is considered total capacity, 5 to 14 is mild incapacity, 15 to 24 is moderate incapacity, 25 to 34 is serious incapacity, and >35 is severe incapacity. The questionnaire will be self-applied and the subject will answer it before the intervention, one week and one month after intervention.

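### The sham laser is specified only as switched off, with no matching of device cues, so On versus Off on participant-reported outcomes may carry an expectation effect

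*Combined protocol and SAP*

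**What the plan says.** Section 3.1 separates the two arms that are needled on the trigger point by laser state alone: "Group On: application of dry needling and LLLT turned on directly on the trigger point" against "Group Off: application of dry needling and LLLT turned off directly on the trigger point". Section 3.5.3 describes the control group's sham in the same terms: "The LLLT equipment will be turned off during the intervention". The abstract also describes the laser as off in both groups.

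The abstract makes On versus Off the contrast of interest: "The hypothesis is that the association of the purposed interventions will have greater effects than only the dry needling intervention". The closing paragraph of the Introduction repeats the question and adds a comparison with placebo.

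Three of the four kinds of outcome in section 3.4 come from the participant. The VAS "will be used so the subjects can graduate their pain in shoulder and neck regions". On the NDI: "The questionnaire will be self-applied and the subject will answer it before the intervention, one week and one month after intervention". PPT is the pressure at which she says that the sensation has become painful. The fourth, surface EMG, is recorded by instrument.

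Section 3.5.2 describes the laser by its physical settings ("wavelength of 830 nm, fluency of 20 J/cm², 30 mW, beam area of 0.116 cm²", continuous beam) and its delivery: "The low-level laser therapy (LLLT) will be applied for 30 seconds at one point on the trigger point in upper trapezius". It mentions no display, indicator light, tone or visible timer. No section mentions a cap, disabled output, screen, eye cover or participant masking. The only use of the term double-blind is in the title of a cited study.

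**The concern.** A sham has to be specified so that the participant's experience is the same except for the active ingredient. This one is specified by switching the device off, and a site that follows the text has no instruction to match anything that goes with a running device. The beam itself need not reveal the arm, since 830 nm is in the near infrared, outside the usual visible range. A panel light, a start or end tone, or a running timer could do so.

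On and Off receive identical needling, so laser state is their only planned difference. Any cue that comes with a running device is therefore completely confounded with emission. Neither randomisation nor the two-way ANOVA in section 3.6 can separate the two. Each woman has a single session, so the problem cannot be repaired once data are collected.

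Off versus Control is not exposed to this cue, because the laser is off in both.

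**Working it through.** **What the plan allows to be checked.** Section 3.3 gives 20 per group, and 3 × 20 = 60 agrees with the stated total. The size is described as a convenience sample. No effect size, standard deviation (SD) or power is given, so there is no power calculation to reproduce.

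**Inputs for the illustration**
- n = 20 per arm (section 3.3).
- Significance at 0.05 (section 3.6). Sidedness is not stated, so two-sided is assumed.
- Laser with no true effect (assumed, to isolate the bias).
- VAS SD of 1.5 or 2 points (assumed).
- Average On-minus-Off expectation shift b of 0.25, 0.5 or 1.0 VAS points (assumed).
- A two-sample t-test at one time point, as a simplification. The plan itself uses a two-way ANOVA, with five VAS times.

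**Formula.** The noncentrality is δ = (b / SD) × √(n/2) = (b / SD) × √10, with 2 × 20 − 2 = 38 degrees of freedom. The false-positive rate is P(T > t) + P(T < −t), where T is noncentral t with parameter δ and t is the 97.5% point of the central t distribution with 38 degrees of freedom. With b = 0 this returns 5.0%.

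| Shift b (points) | SD 2: b/SD, δ | Rate | SD 1.5: b/SD, δ | Rate |
|---|---|---|---|---|
| 0.25 | 0.125, 0.40 | 6.7% | 0.167, 0.53 | 8.1% |
| 0.5 | 0.25, 0.79 | 12.0% | 0.333, 1.05 | 17.7% |
| 1.0 | 0.5, 1.58 | 33.8% | 0.667, 2.11 | 53.8% |

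The shift b is an average over the arms. If only half of a 1.0-point shift arises, because unmasking is partial, the 0.5-point row applies. If only half of a 0.5-point shift arises, the 0.25-point row applies.

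**For scale.** The true difference detectable with 80% power at this sample size is 0.91 SD, which is 1.36 points at SD 1.5 and 1.82 points at SD 2. All the shifts shown are smaller than that.

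**Laser settings.** A common programme and timer need one consistent set of figures, and section 3.5.2 does not give one. Power × time is 0.030 W × 30 s = 0.9 J, and 0.9 / 0.116 = 7.8 J/cm². The section states 2.3 J and 20 J/cm². Those two agree with each other (2.3 / 0.116 = 19.8) but not with the stated power and time.

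**The case against.** The strongest reply is that the documents nowhere show a cue that a participant could notice. The device model is not named, and section 3.5.2 describes no light, sound or display. A reader might infer that women will in fact know their arm and that the contrast is biased. The documents do not support that, and it is not claimed here.

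A reader might also infer that the sham is an unpowered device. Section 3.5.3 refers first to the equipment and then to the laser as being off, and the abstract and section 3.1 refer to the LLLT, so the text does not settle whether power or only emission is off.

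Some design features limit unmasking. Treatment is one session, so no woman experiences both device states. The application is brief and on the upper trapezius, and the documents do not say whether she can see the probe or console. Off participants are also really needled on the trigger point and have reason to feel treated. Consent pages are absent from this copy, so what women are told about an inactive laser cannot be checked.

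The rates above rest on an assumed shift and SD and on a simpler test than the planned one. It would also go too far to say that no positive result could be credited to the laser: surface EMG is less open to belief, and no primary outcome is designated.

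All of this stands, and it makes the concern conditional. It does not remove it, because the text as written leaves the arms free to differ in more than emission and states no safeguard.

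**Conclusion.** The concern holds in conditional form. The sham is specified only by the laser being off, with no cue matching and no participant masking stated. A method that holds everything but emission constant is available and cheap. If a running device gives a perceptible cue, On versus Off on VAS, NDI and PPT may carry an expectation effect. EMG is less exposed, and Off versus Control is not exposed to this cue.

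Neither the presence nor the size of the effect can be taken from the documents. Under the stated assumptions, the false-positive rate for a single VAS comparison would be about 7-8%, 12-18% or 34-54% for average shifts of 0.25, 0.5 or 1.0 points. The change should be made before data collection. Confidence is medium, because the mechanism depends on device features that are not described.

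**What to change.** In sections 3.1 and 3.5.3, replace the switched-off sham with an emission-disabled one:
- In all three arms, use the same device with the same start, timer and sounds, and hold the probe in place for the same time.
- In Off and Control, block or disable emission out of the participant's view, for example with an opaque cap on the probe or, if the device allows it, with the output disabled.
- Use the same eye cover or screen in every arm.
- Before the common programme is set, reconcile the power, time, energy and fluence figures in section 3.5.2. Which of them should stand is for the investigators to decide.

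Optionally, ask each woman after treatment which laser condition she thinks she received. The steps above cannot by themselves show whether masking worked.

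Cost: wording in two sections, a cap and an eye cover or screen, with no extra participants, visits or staff. The small downside is a cap or output check before each session, so that no On participant is treated with emission blocked and no Off or Control participant with it live.

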3.6. Statistical Analysis

Data analysis will be performed through the GraphPad Prism[®] software, version 6.01 (GraphPad Software, La Jolla, California, USA). The Shapiro-Wilk test will be run to verify sample normality distribution. The Two-Way ANOVA test will be used for comparative analysis inter and intra-groups. The P value ($p < 0.05$) will be used to establish the significance of the results, in addition to the 95% Confidence Interval (95% CI). The values will be described as a mean \pm standard deviation.

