These effects can be explained on the red light spectrum, near to infrared (660nm-905nm), have good effects to reduce inflammation, relieve pain, and accelerate the tissue regeneration (22). According to Gerwin (4), 2010, the LLLT has level B of the recommendation of probable effect on the treatment of pain caused by myofascial trigger points. Gattie et al (23), 2017, in their systematic review, state that the current information on dry needling intervention, whether compared to placebo treatment or when compared to another intervention, has very low to moderate quality of evidence. Furthermore, although the trigger points demonstrate changes in muscle activation obtained through electromyography (EMG), there are few studies that present EMG findings in order to demonstrate the effects of dry needling directly on muscle activity (24,25)

In this context, the present study aims to answer if the association of dry needling and photobiomodulation will have a greater effect on the treatment of myofascial trigger points than the dry needling alone or the placebo treatment.

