2.2. Specific Objectives

To evaluate the pain level before, during, and after the dry needling and photobiomodulation applications on the trigger point.

To identify the pain pressure threshold before and after dry needling and photobiomodulation applications on the trigger point

To verify the electromyographic activity of upper trapezius before and after the proposed treatments

To compare the effects fond intra and inter-groups for the applications of dry needling, dry needling and photobiomodulation, and control protocol.

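### Section 3.6 names a two-way ANOVA for outcomes read repeatedly on the same women without making time a within-woman factor or adjusting for the baseline reading

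*Combined protocol and SAP*

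**What the plan says.** Section 3.6 is the whole analysis plan. On inference it says: "The Two-Way ANOVA test will be used for comparative analysis inter and intra-groups". It also names the software, a Shapiro-Wilk check, a 5% significance level with 95% confidence intervals, and description by mean and SD. It does not name the two factors, a subject term, a repeated-measures or matched form, an error term, a sphericity correction, a follow-up contrast or a role for the baseline reading. No other section supplies these.

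The data are repeated readings on the same women (section 3.4 unless stated):
- VAS: baseline, then "soon after the intervention (T₁), 30 minutes after the intervention (T₂), one week (T₃) and one month (T₄) after the intervention", which makes five readings.
- PPT: "This measured will be obtained before the intervention (baseline), soon after the intervention (T₁), and 30 minutes after the intervention (T₂"), which makes three.
- NDI: "the subject will answer it before the intervention, one week and one month after intervention", which makes three.
- EMG: section 3.4 gives no time points. Section 2.2 gives the aim: "To verify the electromyographic activity of upper trapezius before and after the proposed treatments". Two readings are assumed here.

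Section 2.2 also lists pain during the applications. Section 3.4 schedules no such reading, so it is not counted.

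The last objective in section 2.2 is "To compare the effects fond intra and inter-groups for the applications of dry needling" and the other protocols. The Introduction asks whether the combination "will have a greater effect on the treatment of myofascial trigger points than the dry needling alone or the placebo treatment".

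**The concern.** A two-way ANOVA on group and time can be run in two ways. One treats every reading as independent and uses a single residual. The other treats readings as repeated within a woman, tests group against between-woman variation, and tests time and group by time against within-woman variation. Section 3.6 does not say which is meant.

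The choice matters because the errors of the first form run in opposite directions. Its residual mixes the two sources of variation, so the group test rejects too often and the group-by-time test too rarely. The treatment effect lies in group by time, because the group main effect averages in a reading taken before treatment. Two analysts who both follow section 3.6 could therefore reach different conclusions from the same data. The second form is sound in principle, but it assumes sphericity when there are three or more readings. In neither form does the plan say what variance the On-versus-Off comparison uses, or that the baseline reading is used to sharpen it.

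**Working it through.** **Inputs.** Three groups of 20 women (section 3.3); k = 5 for VAS, 3 for PPT and NDI (section 3.4), 2 for EMG (assumed, one value per assessment); 5% level (section 3.6). The documents give no SD, correlation or effect size, so these are assumed: normal outcomes, SD 1 at every reading, equal within-woman correlation ρ of 0.2/0.5/0.8, and for power a 0.8 SD shift. The plan has no power or error calculation to reproduce; 3 × 20 = 60 agrees. The rates below come from simulation, with formulas as a check.

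**1. Expected mean squares with equal correlation.** Between women: 1 + (k−1)ρ. Within women: 1 − ρ. An analysis with independent readings pools 57 and 57(k−1) degrees of freedom:

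[57(1 + (k−1)ρ) + 57(k−1)(1 − ρ)] / 57k = 1.

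So the group F is multiplied by about 1 + (k−1)ρ, and the group-by-time F by about 1 − ρ.

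**2. Group main effect, independent readings.** Type I error ≈ P(F > F_crit / [1 + (k−1)ρ]). For VAS at ρ = 0.5 this is P(F(2, 285) > 3.03/3.0 = 1.01), about 37%.

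| Outcome | k | Error df (57k) | Multiplier at ρ 0.2/0.5/0.8 | Type I error (simulated) |
|---|---|---|---|---|
| VAS | 5 | 285 | 1.8/3.0/4.2 | 19/37/48–49% |
| PPT, NDI | 3 | 171 | 1.4/2.0/2.6 | 11/22/32% |
| EMG | 2 | 114 | 1.2/1.5/1.8 | 8/13/19% |

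With time as a within-woman factor the same test holds about 5% at every ρ.

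**3. VAS group by time, independent readings.** The critical value is 1.97 on 8 and 285 df. To be rejected, a correctly scaled F must exceed 1.97/(1 − ρ), that is 2.46/3.94/9.85. Type I error is 1.4/<0.1/<0.1%.

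Power, with On alone shifted by 0.8 SD at all four post-treatment readings: the interaction sum of squares is 20 × 0.8² × (2/3) × (4/5) = 6.83. Against within-woman error at ρ = 0.5 the noncentrality is 6.83/0.5 = 13.7 on 8 and 228 df, giving 73–74%. With independent readings, simulation gives about 14%. From ρ = 0.2 to 0.8 the pair runs from 30% against 49% to 2% against 99%.

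**4. VAS group by time, repeated measures without correction.** Type I error is about 6–9% under AR(1) correlation of 0.5–0.9. It is about 7–10% if readings in the same session correlate 0.8–0.9 and all others 0.3–0.6. With Greenhouse-Geisser it is about 5% in each case. Two-reading EMG cannot violate sphericity. For PPT, all of whose readings fall around the one treatment session, equal same-session correlations satisfy sphericity and the inflation is nil. For PPT and NDI generally it depends on the correlation assumed.

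**5. On versus Off at one post-treatment visit, 0.8 SD.** Standard errors at ρ 0.2/0.5/0.8:
- Change from baseline, as the pooled residual would have it: √(4/20) = 0.447 throughout.
- Change from baseline, true: √(4(1 − ρ)/20) = 0.400/0.316/0.200.
- Baseline-adjusted: √(2(1 − ρ²)/20) = 0.310/0.274/0.190.

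| Contrast | Power at ρ 0.2/0.5/0.8 |
|---|---|
| Change, pooled residual | 42/40/36% (type I error 2.8/0.6/<0.1%) |
| Change, that visit's own variance | 50/70/98% |
| Baseline-adjusted | 71/81/98% |

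**The case against.** The strongest reply is that the plan promises comparisons within as well as between groups and schedules a baseline and follow-up readings on the same women, so a repeated-measures analysis is the natural reading. This largely stands. A reader might infer from section 3.6 that the trial will treat the readings as independent; the text does not prescribe that, and the large figures apply only if it happens. But the wording promises a comparison over time without saying that readings are linked within a woman, and even the favourable reading leaves sphericity, the On-versus-Off variance and the baseline unaddressed.

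Second, the 48% belongs to the group main effect, which is not the right test of treatment. A reader might take it as the trial's false-positive rate. It is not: under the same reading group by time is conservative, and the harm there is lost power, whose size depends on the assumed effect and correlation.

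Third, two further inferences are tempting and unsupported. One is that the VAS entry range in section 3.3.1 narrows the baseline outcome and so makes variances unequal. That criterion concerns neck and cervical pain over the previous 30 days, while the outcome in section 3.4 is shoulder and neck pain before the intervention; the documents do not say they are the same reading. The other is that the sphericity inflation seen for VAS carries over to PPT and NDI; that depends wholly on the correlation assumed and may be nil.

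Fourth, the EMG figures need one value per assessment at two times. Section 3.4 records four contractions and does not say how they are combined, so those figures are the least secure.

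**Conclusion.** The point holds as a should-fix omission. Run literally with independent readings, the named test is invalid for these data: a group main effect would be declared far too often, and the test that carries the treatment effect would be nearly disabled. The plan does not commit to that reading, and a repeated-measures intent is plausible. In that case the remaining distortion is modest: about 6–10% instead of 5% for VAS group by time if uncorrected, and possibly none for the other outcomes. On either reading, a baseline-adjusted comparison of On with Off uses data already scheduled and gains power over change scores at low and moderate correlation (71% against 50%, 81% against 70%), with little difference at 0.8. The direction of the errors follows from the design; every size rests on the assumed normality, equal SDs, correlations and 0.8 SD effect, with complete data.

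**What to change.** Replace the ANOVA sentence in section 3.6 with wording such as:

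*Each outcome will be analysed by two-way repeated-measures ANOVA with woman as subject, group between women and time within women. The treatment effect will be tested by the group-by-time interaction, Greenhouse-Geisser corrected where there are three or more readings. Between-group differences at each post-treatment visit, including On versus Off, will be adjusted for the baseline reading, use the variance at that visit and be given with 95% confidence intervals. Before/after comparisons within a group will be paired.*

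A mixed model for repeated measures with woman as subject and one common baseline mean across the randomised groups is an acceptable alternative, and it also keeps women who miss a reading. The EMG time points, and how the four contractions form one value, should be stated so that the same model can be applied.

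The cost is one or two sentences and possibly a package other than the one named. No extra participants, visits or measurements are needed.
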